3. **Data collection:** We will compare maternal and fetal free radical mediated oxidative stress between O₂ and RA groups by measuring MDA and 4-HNE in maternal and umbilical cord blood and placenta samples. Maternal blood will be drawn at time of randomization and within 1 hour of delivery. Per the BJH universal cord gas policy, a segment of the umbilical cord and placenta will be removed after delivery of the infant and trained providers will immediately collect UA and umbilical vein samples for routine cord gas analysis. An additional UA sample will be collected for the purpose of this study. We will employ the services provided by the WUMC Women and Infants Health Specimen Consortium to collect samples in EDTA tubes, centrifuge them, and store the plasma in-80°C freezers.
4. **Outcome:** The *primary outcome* is mean maternal and UA MDA and 4-HNE at time of delivery. We will collaborate with the Washington University at St Louis (WUSTL) Core Laboratory for Clinical Studies (CLCS) to perform the Thiobarbituric Acid Reactive Substances (TBARS) assay for MDA quantification[24, 56] This assay is performed by adding TBA to plasma and performing an ELISA to fluorometrically measuring the resultant MDA-TBA complexes. The CLCS will use the commercially available OxiSelectTM TBARS Assay Kit (Cell Biolabs, Inc) to perform these studies. We will use the OxiselectTM HNE ELISA kit (Cell Biolabs, Inc) to quantify 4-HNE. 4-HNE quantification in placental villi will be determined using immunohistochemistry (IHC). Secondary outcomes include UA cord gases and clinical measures of neonatal morbidity including NICU

admission, neonatal death, intubation, mechanical ventilation, hypoxic ischemic encephalopathy, meconium aspiration syndrome and need for hypothermia therapy.

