5. Data analysis: The primary analysis will be by intention-to-treat. Baseline demographics and secondary outcomes will be compared between RA and O₂ groups using χ^2 , Fisher exact test, Mann-Whitney *U* test, or Student's *t* test as appropriate. The primary outcome, mean maternal and UA MDA, will be compared between groups using the Student's *t* test if normally distributed. If non-normally distributed, the median maternal and UA MDA levels will be compared between groups using the Mann-Whitney *U* test. Linear regression will be used to adjust for relevant covariates. We will perform supplementary analyses including 1) stratified analysis by presence of maternal comorbidities or fetal growth restriction to assess if the effect of O₂ on oxidative stress varies in patients with fetal growth restriction or comorbidities. (2) as-treated analysis to determine whether compliance with the assigned group affects outcomes.
6. Sample size calculation: Based on pilot trial data, the mean UA MDA in 33 patients receiving O₂ for Category II EFM in active labor is $8.3 \pm 2.0 \mu\text{M}$. Assuming a two-sided alpha of 0.05, a total **212 patients (106 O₂ and 106 RA)** will afford 80% power to detect a 10% difference mean UA MDA between O₂ and RA groups, while accommodating for 15% loss due to UA samples. A 10% difference in UA MDA levels may be meaningful as neonatal MDA differences as small as 3-5% are associated with free-radical mediated injuries such as hypoxic ischemic encephalopathy [28, 57] There is limited published data on maternal MDA levels and associated adverse outcomes. However, this sample size will afford >90% power to also detect a 10% difference in maternal MDA between groups. To accommodate a compliance run-in of 6 patients, a total of **218 patients** will be recruited.

Feasibility of the sample size: BJH delivers approximately 4,000 patients per year. Based on results of our pilot trial, 32% of the approached patients meeting eligibility criteria consented to participation in the study. Of the patients enrolled, 40% met criteria for randomization (Category II EFM necessitating intrauterine resuscitation after 6cm dilation). In total, 114 patients were randomized over the study period of 12 months. Therefore, we anticipate successful enrollment of 212 patients within 2.5 years (70-72 patients/year).

Secondary Aim 1:

Investigate the relationship between duration of RA or O₂ exposure and magnitude of oxidative stress

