1. Background, rationale, and hypothesis: Khaw et al demonstrated a dose response relationship between maternal MDA concentration and duration of O₂ exposure in a RCT of patients randomized to 60% O₂ by facemask or RA during scheduled cesareans [10]. In an analysis of 27 maternal MDA samples among patients randomized to O₂ in our pilot trial, we found higher median MDA levels in patients who received O₂ for 30-60 mins compared to those who received O₂ for <30 mins. This trend in maternal MDA, particularly in the first 60 minutes of O₂ exposure, suggests a dose-dependent relationship between

duration of O₂ exposure and maternal oxidative stress (unpublished, [name] et al). Here, we will test the hypothesis that duration of O₂ exposure correlates with levels of maternal MDA and 4-HNE.

2. Data collection: Study staff will draw maternal blood at time of randomization and within 1 hour of delivery. Because patients will be randomized to O₂ or RA when they have Category II EFM at any point after 6cm cervical dilation, durations of exposure will vary within groups. Since it is not feasible to sample the umbilical cord at multiple time points, this analysis will be restricted to maternal MDA and 4-HNE.
3. Outcome and data analysis: The primary outcome is mean maternal MDA and 4-HNE in O₂ exposed patients. We will compare mean MDA and 4-HNE across 5 pre-specified durations of O₂ exposure (<30 mins, 30-45 mins, 45-60 mins, 60-90 mins, or >90 minutes) using the one-way ANOVA test. If results of the ANOVA test suggests unequal means, the Tukey post hoc test will be used to identify the groups that differ. Linear regression will also be used to assess the effect of duration of exposure on MDA and 4-HNE concentrations.
4. Estimated statistical power: Maternal MDA differed significantly between 22 patients exposed to O₂ for <30 mins and 20 patients exposed to O₂ for 30-60 mins (unpublished, [name] et al). Based on these data we estimate that the sample size of 212 (106 in the O₂ group) will provide adequate power to detect differences between at least 2 of the 5 groups.

1. .

Secondary Aim 2: Determine the relationship between maternal serum and urine markers of oxidative stress during labor

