|--------------------------------|--|
| Maternal blood (serum) | -At randomization (active labor with Category II EFM) -Within 1 hour of delivery |
| Umbilical artery blood (serum) | -At delivery |
| Maternal urine | -On admission or at enrollment (prior to labor onset) -At randomization -Within 1 hour of delivery |

3. Outcome and data analysis: The primary outcome is MDA and 4-HNE urine concentrations. The primary outcome will be compared between room air and O₂ groups using Student's t test or Mann-Whitney *U* test, as appropriate. Linear regression will be performed to test the correlation between serum and urine concentrations. The mean MDA and 4-HNE urine concentrations throughout the three time points in labor (Table 3) will be graphed to assess baseline trends in oxidative stress over time within the room air group.
4. Estimated statistical power: Due to the exploratory nature of this aim, we will use a sample size of convenience and perform urine assessments in 100 patients (50 room air and 50 O₂). This aim will only include patients undergoing induction of labor, which comprises 70% of our cohort. These results will provide preliminary data regarding the feasibility of urinary oxidative stress analysis in labor and may allow for future oxidative stress studies to maximize patient participation by limiting invasive blood draws.

Safety Monitoring: The study team will review all neonatal adverse events and establish a data and safety monitoring board (DSMB), which will meet after 50% of participants have been recruited to review any adverse neonatal or maternal events among the study cohort and determine safety of continuing the study to completion. Reportable severe adverse neonatal outcomes include intrapartum stillbirth and neonatal death. Reportable non-severe adverse neonatal outcomes include need for hypothermia protocol, seizures, and prolonged NICU stay >72 hours. The study statistician will perform an interim analysis after 50% recruitment. The Haybittle-Peto stopping rule will be used in which a *p* <0.001 for the difference in the primary outcome between groups will guide further conduct of the trial.

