4. Importance of the Knowledge to be Gained- If our hypothesis is confirmed that O₂, compared to RA, increases oxidative stress in laboring patients with Category II EFM, the results will revolutionize labor management for millions of patients annually. Room air would be a safer, perhaps more cost-effective, intervention for management of Category II EFM. Furthermore, knowledge about the relationship between duration of O₂ exposure and oxidative stress will guide future use of O₂ on Labor and Delivery. The data collected on neonatal morbidity will provide more information on the risks of O₂ exposure and guide future larger studies. Findings from this research will be published in peer-reviewed medical journals and presented at local, national, and international conferences.

5. Data and Safety Monitoring Plan- Data and research monitoring will be undertaken annually by the study's PIs and the WUSM IRB. Additionally, a Data and Safety Monitoring board (DSMB) will be established. The DSMB plan includes, but is not limited to, the following features:

Review of adverse events: All personnel in contact with participants and/or data are prepared to identify adverse events and have been instructed to report their occurrence immediately to the study PIs.

Reporting of serious adverse events: In the unlikely event of a serious adverse event, the PIs, in collaboration with any relevant personnel, will take the appropriate actions to report the event to the HRPO/IRB.

Criteria for stopping the study: An interim analysis will be performed after 50% recruitment. Using the Haybittle-Peto stopping rule, a $P < 0.001$ for the difference in the primary outcome between groups will guide further conduct of the trial.

Inclusion of Women and Minorities: We anticipate that the majority of the subjects in this study will be African American. In the recently completed pilot trial, 77% of the patients were African American, 14% were Caucasian, 4% were Hispanic, and 5% were of other ethnicities.

Inclusion of Children: Pregnant minors are considered emancipated under Missouri state law and will be eligible to enroll in the study.

References

1. Hamel, M.S., B.L. Anderson, and D.J. Rouse, *Oxygen for intrauterine resuscitation: of unproved benefit and potentially harmful*. Am J Obstet Gynecol, 2014. **211**(2): p. 124-7.
2. Cruz-Guilloty, F. and V.L. Perez, *Molecular medicine: Defence against oxidative damage*. Nature, 2011. **478**(7367): p. 42-3.

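### Does the p<0.001 interim criterion need amending because it does not say which primary-outcome measure it tests?

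*Combined protocol and SAP*

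**What the plan says.** Safety Monitoring provides one look: "The study statistician will perform an interim analysis after 50% recruitment". A p-value below 0.001 "for the difference in the primary outcome between groups will guide further conduct of the trial". The Data and Safety Monitoring Plan repeats the rule under the label "Criteria for stopping the study: An interim analysis will be performed after 50% recruitment" and the phrase "Using the Haybittle-Peto stopping rule". Neither place names a measure.

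Primary Aim 1 describes its primary outcome twice. Item 4 (Outcome) says it "is mean maternal and UA MDA and 4-HNE at time of delivery", which makes four measures. Item 5 (Data analysis) says "The primary outcome, mean maternal and UA MDA, will be compared between groups", which makes two. Item 6 (Sample size calculation) sizes the trial on UA MDA and adds that maternal MDA has more than 90% power.

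Two secondary aims reuse the label for their own endpoints. In the duration-of-exposure aim, "The primary outcome is mean maternal MDA and 4-HNE in" refers to oxygen-exposed patients only. In the urine aim the text is "The primary outcome is MDA and 4-HNE urine concentrations. The primary outcome will be compared between room air and" oxygen groups.

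**The concern.** A stopping criterion should give one answer for one set of data. This one refers to a primary outcome that has more than one component and two listings, without a rule for combining them. The same interim data could meet it on maternal MDA and miss it on UA MDA. Someone could then choose the reading after seeing the results. If recruitment ended because maternal MDA had crossed, UA MDA, the measure on which the trial is sized, would be left with about half its planned samples.

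**Working it through.** **Inputs.** Maternal MDA: mean 6.5, SD 1.0, n=27 (Primary Aim 1, item 2). UA MDA: mean 8.3, SD 2.0, n=33; two-sided alpha 0.05; 80% power; 10% difference; 15% UA loss; 106 per arm (item 6). The plan gives no maternal–UA correlation and no 4-HNE SD. The oxygen-arm pilot SDs are applied to both arms, with normal data and t tests.

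**1. The plan's own figure.** n per arm = 2(1.960+0.842)² × 2.0² / 0.83² = 91.2, rounded up to 92. Then 92 × 1.15 = 105.8, rounded to 106, so 212 in total. The sample size therefore comes from UA MDA alone. Maternal MDA (standardised difference 0.65/1.0 = 0.65) has about 99% power with 92 per arm, consistent with the plan's statement.

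**2. Samples at the look.** 212/2 = 106 patients, or 53 per arm. For UA, 53 × 0.85 = 45 per arm.

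**3. Observed difference needed for two-sided p=0.001**, from t(0.9995, 2n−2) × SD × √(2/n):
- Maternal MDA, n=53: 0.658, and 0.658/6.5 = 10.1%.
- UA MDA, n=45: 1.435, and 1.435/8.3 = 17.3%.

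**4. Chance of crossing if the true differences are 10%** (noncentral t):
- Maternal MDA, d=0.65: 0.487. Over the 95% interval of the pilot SD (0.79 to 1.37) this runs from 0.80 down to 0.18.
- UA MDA, d=0.83/2.0=0.415: 0.084. Over its SD interval (1.61 to 2.65) this runs from 0.18 down to 0.03.

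**5. Either or both MDA measures** (200,000 simulated trials, true differences 10%, correlation assumed):

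| Correlation | Either crosses | Both cross | Rules disagree |
|---|---|---|---|
| 0 | 0.534 | 0.041 | 0.493 |
| 0.5 | 0.502 | 0.067 | 0.434 |
| 0.8 | 0.492 | 0.081 | 0.410 |

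Disagreement falls to 5–6% at true differences of 5%, and to 0.2% with no effect.

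**6. False crossing with no effect.** One measure: 0.001. Any of two independent measures: 1 − 0.999² = 0.0020. Any of four: 1 − 0.999⁴ = 0.0040. Positive correlation lowers these, and requiring all measures to cross gives less than 0.001. For a single measure, a look at 0.001 followed by a final test at 0.05 gives an overall error of 0.0502.

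**7. Stopping on maternal MDA alone.** At true differences of 10%, UA MDA would reach p<0.05 in 49% (correlation 0), 65% (0.5) or 76% (0.8) of trials with a maternal crossing. The low end is simply the power of UA MDA with 45 per arm.

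**8. Which text competes.** The criterion concerns a difference between randomised groups. That rules out the duration endpoint, which compares exposure categories within the oxygen arm. The urine endpoint does compare arms, but it belongs to an aim the plan calls exploratory, in a convenience sample of 100 induced patients. Context leaves Primary Aim 1. The contrasts in steps 3 to 5 are between two MDA measures that appear in both of its listings, so they show the missing one-or-all rule and not the four-versus-two discrepancy. The effect of that discrepancy cannot be computed from the documents.

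**The case for a change.** The strongest case for amending is that the remedy costs almost nothing: one agreed listing and one sentence in two places, with no effect on sample size, assays or the adverse-event review. The rule sits under stopping criteria, so somebody must declare whether it was met. At the plan's own 10% differences, the either and both readings give opposite answers in 41–49% of trials.

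Much of this stands. The two listings differ, the one-or-all rule is absent, and the readings are not interchangeable if the effects are as large as planned. It is good practice for the statistician to write down the measure and the crossing rule before running the analysis.

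It does not carry a change to the plan. The 41–49% holds only if both true differences are 10%. A disagreement decides nothing by itself, because the criterion informs a judgement and whoever makes it would see both MDA results. The loss of UA information in step 7 arises only if recruitment is actually ended on a maternal crossing, which no text requires. A replacement sentence would also need blanks for the measure and the rule. UA MDA alone, both MDA measures or a fixed order would all be workable, and the documents do not rank them. Nor do they say whether the look has already taken place.

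**Conclusion.** The concern points to a real gap in wording, but one that analysts can fill sensibly. Read in context, the criterion belongs to Primary Aim 1, and the sample size basis makes UA MDA the natural default. The threshold is strict enough that false crossing stays at or below about 0.004 however the Primary Aim 1 measures are combined. No stop is mandated, and not crossing leaves the final analysis as planned. The DSMB's review of neonatal and maternal adverse events does not depend on the criterion.

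What remains is a difference in the chance of an early signal: about 49% on maternal MDA against 8% on UA MDA at true 10% differences. Those figures rest on pilot SDs from 27 and 33 oxygen-exposed patients and on 15% UA loss at the look. The either/both figures also rest on assumed correlations. No change to the plan is needed.

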Our central hypothesis is that prolonged intrauterine exposure to O₂ during labor, compared with room air (RA), generates free radicals that have downstream biochemical and clinical consequences to the neonate. This hypothesis is founded on several lines of evidence. First, neonatal resuscitation *post-delivery* with 100% O₂ is associated with an increased risk of free radical disease including retinopathy, hypoxic ischemic encephalopathy, and cerebral palsy (6). Second, preliminary studies on *intrapartum* O₂ administration suggest possible harm to the fetus. In patients undergoing scheduled cesarean deliveries, administration of just 60% O₂ was associated with increased free radical activity in both the mother and fetus (8). In other small clinical trials comparing O₂ to RA in laboring women, those receiving O₂ were up to four times more likely to have neonates with decreased umbilical artery pH and an increased need for delivery room resuscitation. (4,5) However, none of these studies investigated mechanisms for harm with excess O₂ *during labor* or neonatal consequences, such as neurodevelopmental outcomes, past the delivery room. (7) Third, our preliminary data from a large observational cohort showed that intrauterine hyperoxemia, compared to normoxemia, was associated with an increased risk of neonatal morbidity in acidemic neonates. Finally, prior animal and human magnetic resonance imaging (MRI) studies have demonstrated distinct changes in the hypothalamus, hippocampus, and white matter in neonates exposed to O₂ *after birth*, revealing potential regions of the brain susceptible to hyperoxia-associated injury mediated by free radicals (7-9). Taken together, these data suggest that the use of RA for intrauterine resuscitation may be safer than O₂. Analysis of a recently completed pilot RCT at our institution comparing O₂ to RA in laboring women with Category II EFM demonstrated feasibility of a randomized trial in this setting. Therefore, we will test our hypothesis by pursuing the following specific aims:

Primary Aim: Conduct a randomized controlled trial of maternal O₂ supplementation versus RA in patients with Category II EFM in labor to:

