Although several markers of oxidative stress exist, MDA and 4-HNE are particularly relevant as it has been linked to both adult and neonatal morbidity. In adults, increased MDA levels are associated with "disruption of surface receptor pathways and clinical diagnoses such as atherosclerosis and cardiovascular disease [25, 26]. Elevated MDA levels in the neonate are associated with hyperbilirubinemia and hypoxic-ischemic encephalopathy [27-29]. There is also evidence that MDA can be transplacentally transported and thus, the mother and fetus are at risk for downstream effects [30]. Elevated 4-HNE is associated with injury to developing neurons^{34,35} and has been implicated in the pathogenesis of morbid diseases such as Alzheimer's disease, atherosclerosis, and malignancy.

Excess intrauterine oxygen exposure may be harmful to the neonate: Several studies evaluating hyperoxygenation in adults and animals have demonstrated detrimental cardiac, pulmonary, and cerebral effects [16, 31-34]. Over-oxygenation in neonates is associated with free radical diseases including retinopathy, bronchopulmonary dysplasia, hypoxic ischemic encephalopathy, and cerebral palsy [1, 5-9]. As a result, the American Academy of Pediatrics now recommends initial neonatal resuscitation with room air (RA) instead of O₂[35]. The detrimental postnatal effects of hyperoxia call for a closer look at intrauterine O₂ exposure. The two small published clinical trials comparing O₂ to RA in laboring patients with reassuring EFM found that more neonates in the O₂ group required delivery room resuscitation and that O₂ exposed neonates were more likely to have umbilical artery (UA) pH values <7.20 [11, 12]. Our preliminary data also suggest an increased risk of neonatal morbidity in acidemic neonates with hyperoxia (see C1-1)[36]. The results of these

Figure 1: Oxidative stress and production of malondialdehyde

clinical studies raise important safety questions about risks to the neonate with liberal use of intrapartum O₂ but do not address the primary indication for O₂ use: Category II EFM.

Research Design and Methods

Overview

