Anticipated challenges and safeguards: A potential limitation of the study is the inability to blind patients and healthcare providers to the allocation, however, the assessors will be blinded to allocation to limit bias in data analysis. Allocation concealment via use of opaque sealed envelopes will also limit selection bias. Bias could result from nurses and physicians managing subjects differently based on knowledge of their group assignment. To minimize this, providers will be specifically instructed to apply all other intrauterine resuscitation techniques as needed, irrespective of their group assignment. Any additional intrauterine resuscitation that is performed will be documented. To maximize adherence to protocol, we will conduct nursing and physician education sessions.

Protection of Human Subjects/Approvals

1. Risks to human subjects-

1A. Human subjects' involvement, characteristics, and design- The study will enroll 212 patients to investigate whether intrapartum O₂ administration in patients with Category II EFM is associated with oxidative stress. The study population will be English-speaking. Amongst the patients enrolled in the pilot trial, 77% were African American, 14% were Caucasian, 4% were Hispanic, and 5% were of other ethnicities. [name] and the other study members have completed the training module required by the WUSM Human Research Program Office and received education on the responsible conduct of research. The preceding pilot trial was approved by the IRB at WUSTL (IRB ID 201602164) and registered at ClinicalTrials.gov (ID NCT02741284).

1B. Sources of materials-

The study will involve collection of data from two key components:

- 1) Clinical Data Collection** from the medical records of mother and child. For all subjects, these data will be stored in a secure, password-protected REDCap database anonymized with study identifier only.
- 2) Maternal and cord blood samples**: All blood samples will be stored in a locked freezer that only the research team has access to. The maternal/ cord blood and placenta outcomes assessed in this study are additional materials collected for the purpose of the study and are not a part of routine prenatal care. Maternal and cord blood/placenta malondialdehyde levels are not used clinically and at present, cannot be directly linked to clinical outcomes. This will be disclosed to all study participants.

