1C. Potential Risks: The proposed study involves potentially rare risks to the subjects, including loss of confidential health information, provision of poor feedback to families regarding outcome data, physical risks of serial blood draws, and excessive demands on patients. We anticipate minimal risk to the neonate by "withholding" oxygen treatment for Category II EFM because (1) the clinical evidence thus far suggests that oxygen provides no benefit, and (2) there were no adverse outcomes amongst neonates in the room air group of my pilot trial. Protections against anticipated risks are outlined below under "Adequacy of Protection Against Risk."

2. Adequacy of protection against risks-

2A. Recruitment and Informed Consent: Pre-screening for eligibility criteria via medical record review will be conducted, and potential participants will be approached on Labor and Delivery. None of the data obtained in pre-screening will be saved. The study design, expectations, and risks/benefits will be explained, and potential subjects will be given a written informed consent form by a study team member. Consent will be documented by using a signed consent form. Trained study team members will have sufficient time to explain the study and the informed consent carefully in a private room, and eligible patients may decide to enroll at any time as long as they still meet eligibility criteria. Of note, our team has significant experience recruiting patients and neonates as part of prior investigations in this population.

2B. Protections Against Risk- Oxygen administration for Category II EFM is the current standard of practice. The safety of randomization to room air for Category II EFM has been demonstrated by the preceding pilot trial. All neonatal adverse events will be reviewed by the data and safety monitoring board (DSMB), which will meet after 50% of participants have been recruited to review any adverse neonatal or maternal events among the study cohort and determine safety of continuing the study to completion. The PI will be responsible for reporting all adverse events to the IRB.

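### A positive oxidative-stress result cannot show that room air is safer, and a pilot of 114 patients cannot have demonstrated that it is safe

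*Combined protocol and SAP*

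**What the plan says.** All places are in the combined protocol and SAP.

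**What a positive result would mean.** Section 4, Importance of the Knowledge to be Gained, sets a condition, "If our hypothesis is confirmed that O₂, compared to RA, increases oxidative stress in laboring patients with Category II EFM", and shortly afterwards draws the consequence: "Room air would be a safer, perhaps more cost-effective, intervention for management of Category II EFM". The condition names oxidative stress only. The same paragraph adds that the neonatal data will inform later, larger studies.

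**What the marker can support.** Section 1B, Sources of materials, says that maternal and cord MDA has no clinical use and at present "cannot be directly linked to clinical outcomes". Participants are to be told this.

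**Status of neonatal morbidity.** Specific Aims labels the neonatal composite exploratory. Primary Aim 1, item 5, lists significance tests for secondary outcomes but names no effect measure or confidence interval. Item 6 bases the sample size on umbilical artery (UA) MDA.

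**What the pilot showed.** Section 2B, Protections Against Risk: "The safety of randomization to room air for Category II EFM has been demonstrated by the preceding pilot trial". Section 1C, Potential Risks, gives two reasons for expecting minimal risk: that the evidence so far suggests oxygen has no benefit, and that "there were no adverse outcomes amongst neonates in the room air group of my pilot trial". Specific Aims says of the same pilot only that it "demonstrated feasibility of a randomized trial in this setting". Its size appears under Feasibility of the sample size: "In total, 114 patients were randomized over the study period of 12 months".

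**The concern.** Section 4 moves from a biomarker difference to a safety conclusion, while section 1B says that the biomarker cannot yet carry that inference. If section 4 is followed as written, a positive MDA result would be presented as showing room air to be safer, although the trial has little ability to detect even a doubling of neonatal morbidity in either arm.

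The 2B sentence has the same fault in the other direction. It treats a zero count in part of a small pilot as proof of safety, in the section that explains why participants are protected when they are randomized away from what 2B itself describes as current standard practice. The documents give no room-air denominator, no definition of an adverse outcome, no count for the oxygen arm and no interval.

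**Working it through.** **1. Reproduce the planned sample size.** Inputs from Primary Aim 1, item 6: UA MDA mean 8.3 µM, SD 2.0, a 10% difference (0.83 µM), two-sided alpha 0.05, power 80%, 15% loss.

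n per arm = 2 × (1.960 + 0.842)² × (2.0/0.83)² = 91.2, rounded up to 92. Then 92 × 1.15 = 105.8, or 106 per arm and 212 in total. This matches the plan. The trial is sized for the marker.

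**2. What 106 per arm can say about neonatal morbidity.** The documents give no base rate, so 1%, 2% and 5% are assumptions. Power is for a doubling in one arm, two-sided alpha 0.05.

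| Assumed rates | Fisher exact power, 106 per arm | Normal-approximation power | n per arm for 80% power (normal approximation) |
|---|---|---|---|
| 1% v 2% | 1% | 9% | 2319 |
| 2% v 4% | 5% | 13% | 1141 |
| 5% v 10% | 20% | 28% | 435 |

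The last column uses n = [1.960 × √(2p̄(1−p̄)) + 0.842 × √(p₁(1−p₁) + p₂(1−p₂))]² / (p₁−p₂)². For 5% v 10%: (0.730 + 0.312)²/0.0025, which rounds up to 435.

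If no events at all were seen among 106 room-air neonates, the one-sided 95% upper limit would still be 1 − 0.05^(1/106) = 2.8%.

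**3. What zero events in the pilot can say.** The pilot randomized 114 in all. Arm sizes are not stated; 57 on room air is assumed, with a range of 50 to 64. With zero events, the exact upper limit is 1 − 0.05^(1/n) one-sided and 1 − 0.025^(1/n) for a two-sided 95% interval.

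| Room-air neonates | One-sided 95% limit | Two-sided 95% limit |
|---|---|---|
| 50 | 5.8% | 7.1% |
| 57 | 5.1% | 6.3% |
| 64 | 4.6% | 5.6% |
| 114 (extreme case: everyone) | 2.6% | 3.2% |

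The chance of seeing zero events in 57 is (1 − p)^57: 56% if the true rate is 1%, and 32% if it is 2%. Ruling out a 2% rate with zero events (one-sided 95%) takes ln 0.05 / ln 0.98, or 149 neonates; ruling out 1% takes 299.

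**4. The statements side by side.** Section 1B: MDA cannot be linked directly to outcomes. Section 4: an oxidative-stress result makes room air safer. Both cannot stand unqualified. Likewise, Specific Aims credits the pilot with feasibility, while 2B credits it with demonstrated safety.

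**The case against.** **The section 4 sentence is conditional and explains why the research matters.** That is correct: it is not an analysis, decision or reporting rule. A reader might infer that the protocol commits to calling room air safer whatever the neonatal results show. The documents do not say so. Specific Aims speaks more cautiously of room air possibly being safer, the data and safety monitoring board (DSMB) reviews neonatal and maternal events at 50% recruitment, and section 4 itself looks to larger studies. What remains is that the stated condition for the safety conclusion is the marker result alone.

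**The protocol does connect MDA with morbidity.** Background associates raised neonatal MDA with hypoxic-ischemic encephalopathy, and item 6 cites small MDA differences alongside such injuries. These are associations. They do not establish that a between-arm shift in MDA changes outcomes, and they leave section 1B's caveat in place. That caveat names MDA only; the protocol does not extend it to 4-HNE.

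**Background might seem to contradict both safety statements.** It says that the published clinical studies "do not address the primary indication for O₂ use: Category II EFM". Those trials were in patients with reassuring tracings, whereas the pilot enrolled Category II patients. The remark therefore weakens only the premise in 1C that the evidence suggests no benefit from oxygen.

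**The 5.1% limit might be read as risk caused by withholding oxygen.** It is not. It bounds the absolute event rate on room air. The relevant quantity is the excess over the oxygen arm, which cannot be computed because no oxygen-arm count is given.

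**A reader might infer that the pilot claim was used to justify limited monitoring.** No section ties the monitoring schedule to the pilot, and 2B goes straight on to require DSMB review.

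**The zero count comes from 1C, which says only that minimal risk is anticipated.** That also stands: 2B states its conclusion without citing a basis. The 1C count is the only pilot safety result the documents give.

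**Conclusion.** The point holds within these limits. Section 4 draws a safety conclusion from a marker that section 1B says cannot be directly linked to clinical outcomes, and the neonatal data cannot fill the gap: at 106 per arm, Fisher power for a doubling is about 20% from an assumed 5% rate and about 5% from an assumed 2% rate. Section 2B overstates the pilot. Zero events among an assumed 57 room-air neonates leaves a one-sided 95% upper limit of 5.1% (5.8% to 4.6% for 50 to 64). The conclusion does not depend on the split, since even 0 of 114 leaves 2.6%.

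The assumptions are the pilot arm size and the neonatal base rates; neither is in the documents. Nothing here shows that room air is unsafe, and the primary comparison is unaffected. What changes is the conclusion the trial may draw and how neonatal outcomes are reported.

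**What to change.** 1. **Section 4.** State that a positive primary result would show that oxygen raises oxidative-stress markers, and no more. Add that neonatal outcomes will be reported by arm and that the trial is not powered to establish which arm is safer.
2. **Primary Aim 1, item 5.** Add risk differences with 95% confidence intervals for the neonatal outcomes, alongside the tests already listed.
3. **Section 2B, with 1C brought into line.** Replace the claim of demonstrated safety with the pilot's event counts and denominators in both arms, the definition of an adverse outcome, and the between-arm difference with its 95% interval. Giving only the room-air upper limit would invite the misreading described above.
4. **Section 1C.** Qualify the no-benefit premise by noting, as Background does, that the published trials did not study Category II tracings.

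The cost is wording in two sections, intervals on outcomes already collected, and retrieval of the pilot counts. The safety statement becomes less favourable. Sample size, primary test and study procedures do not change.
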